## Study Timeline

Dates	Description
10 February 2024	
 
● Preliminary protocol drafted
 
● Quality performance indicators finalised
 

March 21 2024	
 
● HDEC submission (expedited pathway) in
 
● Tupu grant application in
 

March 27 2024	
 
● Data collection form finalised/ redcap form created
 

April (first week) 2024	
 
● Second general meeting of investigators and protocol finalised
 
● Slide made for NZAGS conference and presented
 
● REDCap users generated and sent to investigators
 

April - June 2024	Centres recruited and locality ethics applications in 
 
● Prepare for data collection
 

01 July 2024	Data upload window opens
30 September 2024	Data upload window ends - REDCap locked for new entries
31 October 2024	30-day follow up from day of admission
November/December 2024-January 2025	Data analysis and manuscript writing

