## Study Summary

Study title	An Aotearoa-New Zealand (AoNZ) multi-centre, prospective cohort study of acute pancreatitis management and outcomes.
Internal ref. no./ short title	PANORAMA Study
Study design	Multicentre prospective observational cohort study.
Study population	Adult patients diagnosed with acute pancreatitis admitted to any public hospital in AoNZ.
Eligible centres	All public hospitals in AoNZ.
Planned cohort	Enrolment for 3 months.
Objective	To measure adherence to quality performance indicators of the early (<72 hours) management of acute pancreatitis (AP) in AoNZ.
Primary outcomes of interest	
 
• Proportion of patients that were managed in compliance with quality performance indicators overall
 

Secondary outcomes of interest	
 
• Variation in compliance with QPIs between hospitals for each of the management domains
 
• Requirement for mechanical ventilation (invasive and non-invasive)
 
• Requirement for renal replacement therapy
 
• Requirement for inotropic or vasopressor support
 
• Intervention for complication of AP
 
• Alive and discharged at 30-days
 

Follow-up	30-days after admission.
Data collection period	1 July 2024 - 30 September 2024

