### 5.3. Data Collection

An investigator at each contributing hospital will be appointed to be responsible for data collection of all appropriate patients. Patients for AP may be admitted under multiple teams, it is the hospital lead's responsibility to capture all patients with AP that occur during the study inclusion period.

Data will be collected and stored using the web application REDCap. This web application is encrypted with HIPAA-Security, compliant with guidelines in the United States, and is widely used by academic institutions.

REDCap is a secure, web-based software platform designed to support data capture for research studies. It provides: 1) an intuitive interface for validated data capture; 2) audit trails for tracking data manipulation and export procedures; 3) automated export procedures for seamless data downloads to common statistical packages; and 4) procedures for data integration and interoperability with external sources.

Clinical data at each participating hospital will only be accessed by medical students and resident medical officers who already have access to the clinical data being collected. Individuals working at other centres, and those without access to patient clinical data, will not be involved in data collection. Locality approval will be sought and obtained at all centres prior to study commencement. An excel spreadsheet will be kept alongside the REDCap database at each hospital. This will be stored on a password protected hospital computer at each hospital. A unique RedCap number will be created for each patient. This number will allow re-identification of patients by the local hospital lead if required. After data has been uploaded into REDCap the local hospital copy of the data will be destroyed to protect patient privacy. An excel spreadsheet containing the REDCap key and the relevant patients NHI will be kept. This excel spreadsheet will allow future patient re-identification if required. During REDCap data upload there will be no data fields where identifiable data can be uploaded; for example, names or NHI's. Local excel files will be stored at each hospital for 10 years and destroyed following this. The central de-identified data set will be stored for 10 years using REDCap electronic data capture tools.

If further studies using this data set are to be performed a subsequent ethics application will be required before its use.

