## 5.6. Follow-up

All patients will be followed for the initial 72 hours following admission into ED by a clinician and then again chart reviewed at 30 days from initial admission.

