## 10. Study completion

### 10.1. Completion

The study will be deemed complete after 4 months (3 months of recruitment and 1 month of follow up) of prospective data collection. The data will then be pooled and analysed by the chief investigator.

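### REDCap closes to new records on the apparent last day of enrolment, so eligible September admissions not opened by then cannot be entered

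*Protocol*

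**What the plan says.** The Study Timeline gives 1 July 2024 as "Data upload window opens" and 30 September 2024 as "Data upload window ends - REDCap locked for new entries". Thirty-day follow-up ends on 31 October, and analysis starts in November.

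The Study Summary gives the data collection period as "1 July 2024 - 30 September 2024" and the planned cohort as "Enrolment for 3 months". Section 10.1 divides the four-month study into "3 months of recruitment and 1 month of follow up". No section states a last eligible admission date separately from the lock.

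On completeness, Section 5.3 notes that patients may be under several teams and says "it is the hospital lead's responsibility to capture all patients with AP that occur during the study inclusion period". The same section sets the first data collection at up to 48 hours after admission. Section 5.6 goes further: "All patients will be followed for the initial 72 hours following admission into ED by a clinician". Section 6.3 says that a REDCap ID is generated when a patient's entry is created, but no section says when an entry must be created.

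**The concern.** Enrolment and the facility to create a record appear to end on the same day. A patient admitted late on 30 September and diagnosed on 1 October is eligible by admission date but has no stated way into the database. The same holds for a patient under a team that the collectors do not routinely see, if the case comes to light only in October. Eligibility itself may not be known on arrival: Appendix B requires two of three features, and one of them is imaging.

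Such losses need not be random. Table 1 in Section 3 makes diagnosis within 12 hours of admission the first quality performance indicator (QPI 1), and a patient diagnosed late fails it. A lock that removes late-diagnosed patients would raise measured adherence to that indicator. The loss could also differ between hospitals according to how soon each opens its records. That would touch the between-hospital comparison and the funnel plots in Section 8, which have the number of admitted patients on the horizontal axis.

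**Working it through.** **1. Do the plan's own dates fit together?**
- 1 July to 30 September = 31 + 31 + 30 = 92 days, which is the stated 3 months.
- 30 September + 30 days = 30 October, inside the stated 31 October. Working back, 31 October − 30 days = 1 October.
- 1 July to 31 October = 92 + 31 = 123 days, which is the stated 4 months.

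The dates are consistent with admissions running to about 30 September. The grace period between last admission and lock is then 0 days. The end of the admission window is a well-supported inference, not a stated date.

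**2. Share of the window whose early time points fall after the lock**

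Formula: (hours / 24) / 92, assuming even admissions and a lock at the end of 30 September. The timeline gives no clock time, so a lock at the start of that day adds one day to the numerator.

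| Time point | Lock at end of day | Lock at start of day |
|---|---|---|
| 12 h (QPI 1 limit) | 0.5/92 = 0.5% | 1.5/92 = 1.6% |
| 48 h (Section 5.3) | 2/92 = 2.2% | 3/92 = 3.3% |
| 72 h (Section 5.6) | 3/92 = 3.3% | 4/92 = 4.3% |

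These shares are exposure. A patient in them is lost only if no record was opened before the lock.

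**3. Rough count (for scale only)**

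Section 1 gives an incidence of 58 per 100,000 adults per year. The adult population is not in the protocol; assume 3.5 to 4.5 million, with every hospital taking part.
- Expected cases: 58/100,000 × population × 92/365 = about 512 to 658.
- In the last 2 days: about 11 to 14. In the last 3 days: about 17 to 21.
- In 4 days (start-of-day lock, 72 h): about 22 to 29.

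**4. Effect on the overall compliance proportion**

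If a share m is lost and its compliance differs from that of the retained patients by D, the reported proportion is off by m × D. The protocol gives no D; assume 30 percentage points and that everyone exposed is lost.
- 2/92 × 30 = 0.65 points
- 3/92 × 30 = 0.98 points
- 4/92 × 30 = 1.30 points

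**5. Effect on QPI 1 through delayed diagnosis alone**

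A patient diagnosed h hours after admission is shut out by an end-of-day lock only if admitted in the last h hours of the window. The chance of exclusion is therefore (h/24)/92. It rises with the delay, so the selection is real, but at 72 hours it is still only 3.3%. Suppose true adherence is 90% and every failure is diagnosed at 72 hours (both assumptions). Out of 100 patients, 10 × 3/92 = 0.33 failures are removed, and reported adherence is 90/99.67 = 90.3%.

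**6. What cannot be computed**

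The number of July to September cases that collectors find only after 30 September cannot be derived from the protocol.

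**The case against.** The strongest reply is that the lock covers new records only. Existing records must stay editable, since 30-day data are added to them through October, so an entry opened on 30 September can receive its 48-hour and 72-hour data afterwards. Nothing in Section 5.3 or 6.3 makes upload wait until the early data are complete. Cases missed in July, August or most of September can be added on any day up to the lock. All of this stands.

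It rules out several stronger conclusions that a reader might infer:

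- *All end-of-September patients are excluded, or the capture requirement as a whole fails.* Only patients with no record by 30 September are excluded.
- *A hospital uploading 1 or 2 weeks behind loses 7/92 = 7.6% or 14/92 = 15.2% of its patients.* This assumes that no record is opened during the lag. The protocol describes no such lag and puts first data collection within 48 hours.
- *QPI 1 is badly inflated, for example from 90% to 90/95 = 94.7%.* This needs 5% of all cases across the whole window to be lost and every one of them to fail. The lock does not produce that. A case overlooked by a collector is also not the same as a case diagnosed late: a patient under another team may have been diagnosed promptly. For overlooked cases the direction of bias is therefore not established.

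What the reply leaves untouched is the patient admitted by 30 September and recognised in October, for whom no route exists. It might also be said that admissions are meant to stop earlier. In that case the protocol omits the last eligible admission date, and the same edit is needed.

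**Conclusion.** The point holds in a limited form. A stated date rule conflicts with a stated duty: new records stop on the apparent last day of enrolment, while the hospital lead is to capture every case in that period. Exposure from end-of-window admissions is about 2% to 3% of the window, or up to about 4% if the lock falls at the start of the day. Actual loss from this source should be lower, because many of those records will already be open. To it must be added an unknown number of earlier cases found after the lock.

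The loss may be selective for QPI 1 and uneven between hospitals, but the likely effect on overall compliance is about 1 percentage point under the assumed 30-point difference. This rests on even admissions, on the inferred end of the admission window, and on reading the lock as applying to new records only. It does not threaten the study's aims. It is worth correcting because the correction costs almost nothing.

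**What to change.** In the Study Timeline and Study Summary, separate two dates that now coincide:

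- **Eligibility:** by admission date, 1 July to 30 September 2024.
- **REDCap lock for new entries:** 31 October 2024, the follow-up date already planned, for admissions within the eligibility window only. Flag any record opened after 30 September.

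This gives 31 days of grace instead of none. The latest 48-hour and 72-hour points (2 and 3 October) then fall before the lock, and missed cases can still be added. The four-month duration in Section 10.1 and the November start of analysis do not change.

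The cost is one date change and one flag field. The downside is that a few records will be abstracted retrospectively, from the routine notes that Section 6.1 already uses for follow-up. A check of entries against existing hospital lists at the end of the window, and reporting adherence with and without the flagged records, would be optional additions.

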## Study Summary

Study title	An Aotearoa-New Zealand (AoNZ) multi-centre, prospective cohort study of acute pancreatitis management and outcomes.
Internal ref. no./ short title	PANORAMA Study
Study design	Multicentre prospective observational cohort study.
Study population	Adult patients diagnosed with acute pancreatitis admitted to any public hospital in AoNZ.
Eligible centres	All public hospitals in AoNZ.
Planned cohort	Enrolment for 3 months.
Objective	To measure adherence to quality performance indicators of the early (<72 hours) management of acute pancreatitis (AP) in AoNZ.
Primary outcomes of interest	
 
• Proportion of patients that were managed in compliance with quality performance indicators overall
 

Secondary outcomes of interest	
 
• Variation in compliance with QPIs between hospitals for each of the management domains
 
• Requirement for mechanical ventilation (invasive and non-invasive)
 
• Requirement for renal replacement therapy
 
• Requirement for inotropic or vasopressor support
 
• Intervention for complication of AP
 
• Alive and discharged at 30-days
 

Follow-up	30-days after admission.
Data collection period	1 July 2024 - 30 September 2024

# 1. Background and rationale

Acute pancreatitis (AP) is one of the most common gastrointestinal conditions resulting in hospital admission. It has an estimated annual incidence of 58 per 100,000 in Aotearoa-New Zealand (AoNZ) adults (1–3). AP is characterised by a local and systemic inflammatory response with variable clinical progression, from mild to severe as defined by the degree of organ dysfunction (4). The majority of patients with AP suffer only mild disease that is self-resolving. However, 20% develop moderate or severe AP, which involves pancreatic or peripancreatic necrosis, organ failure, or both. Severe pancreatitis is a serious condition with a risk of mortality between 20-40% (5–8). Despite substantial disease burden, there are no effective therapies that alter the course of disease and management remains largely supportive.

In the last decade, a number of landmark clinical trials have provided substantial guidance on the management of the AP, particularly with regards to antibiotic use, endoscopic retrograde cholangiopancreatography (ERCP)(9), and management of necrosis (10,11). Furthermore, multiple scientific bodies have developed and disseminated evidence-based guidelines for managing AP. However, their adoption into clinical practice remains suboptimal. An international cohort study that assessed the compliance rate with current guidelines in the treatment of patients with acute biliary pancreatitis showed a wide variability of practice (12). While it is commonly believed that noncompliance with published guidelines indicates areas in which recommendations are based on insufficient evidence, previous studies have shown a lack of compliance even in areas where randomised controlled trials (RCTs) have already resolved controversial issues during the last 10 years (12,13).

A multicentre national observational study will enable the assessment of compliance to quality performance indicators (QPIs) for the early management of AP in the AoNZ context. Furthermore, it will demonstrate any potential excess morbidity associated with noncompliance to best evidence driven clinical practice. Currently there is no such data for AoNZ. This data can be used to standardise and optimise care nationally to create more equitable outcomes for all patients.

## 2. Aims

### Primary Aim:

To measure adherence with quality performance indicators (QPIs) for the management of AP during the first 72 hours after admission in AoNZ.

### Secondary Aims:

- To measure the variation in compliance with QPIs between each hospital in AoNZ for each management domain for the management of AP during the first 72 hours after admission.
- To correlate compliance (overall and for each management domain) with QPIs and defined clinical outcomes stratified by AP severity.
- To compare clinical outcomes between compliant and non-compliant management of patients stratified by AP severity.

## 3. Quality Performance Indicators

Multiple practice guidelines have been published for the management of AP (14–19). The recommendations in these guidelines are usually based on a systematic review of the relevant literature and the evidence on which is based on the available evidence, which is usually graded. Quality performance indicators will be drawn from these evidence-based recommendations for each of the nominated management domains that are relevant to the management of patients within the first 72 hours from admission to hospital. Any differences in the recommendations between the source guidelines will be resolved by discussion amongst the Scientific Advisory Group and consensus established for the QPIs.

The QPIs were developed for the following management domains: (Appendix D: Table 1 with guidelines)

**Table 1.** Quality Performance Indicators

	Domain	QPI	Ref*	Metrics
1	Diagnosis	All patients diagnosed within 12 hours of admission	IAP	RAC criteria for diagnosis: enzymes 3xUL, typical pain ± CT scan
2	Aetiology	All patients had tests for aetiology determined within 24 hours of admission	IAP	U/S for gallstones ETOH history with intake (units per week, timing of binge to pain) If both negative then lipids, IgG4, drugs
3	Severity (predicted)	All patients had prediction of severity on admission	IAP	N / Y, if yes method (drop-down of all options and other) Further drop-down bar will the give options for severity (mild, moderate, and severe)

4	Severity (actual)	All patients had actual severity determined at 48 hours	-	N / Y, if yes method (drop-down RAC, DBC and other) Further drop-down bar will the give options for severity (mild, moderate, and severe)
5	CT scan	Initial CT assessment performed after 72-96 hours if poor response to initial management or clinical deterioration, unless there is diagnostic uncertainty. Not required for severity prediction.	IAP	N / Y, if yes indication (drop-down with other)
6	Transfer	All patients with predicted or actual severe AP in the first 72 hours are discussed with specialist pancreas service.	Nice	N / Y Indication for transfer (drop-down)
7	Analgesia	All patients given narcotic analgesia within one hour of admission	-	Step-up or step-down approach? IV analgesia given on admission N / Y NSAIDS given to mild AP Analgesics prescribed
8	Fluids	
 
All patients commenced on IV Hartmann's solution within one hour of admission to the emergency department by a clinician and at an initial rate of 5-10 ml /kg in response to hypovolemia until resuscitation goals reached.
 
Then a rate of 1-2 ml/kg/hour for patients not tolerating PO in the first 48 hours.
 
	IAP	IV fluids N / Y Time commenced from admission What initial fluid was given? Initial prescribed rate Initial received rate Average rate 2 nd 24 hours Average rate 3 rd 24 hours Fluid bolus given (# times and and timing) Volume / 24 hours over 72 hours?
9	Anticoagulation	All patients with predicted severe AP considered for or started on anticoagulation within 24 hours of admission	-	Anticoagulation N / Y Medication prescribed When started (hours from admission)
10	Antibiotics	Antibiotic prophylaxis not recommended for the prevention of infectious complications in AP	IAP	Antibiotic N / Y Antibiotic indication

11	Nutrition	
 
1. No patients made 'nil-by-mouth' and no food withheld unless there was a clear reason.
 
2. Offer EN to anyone with MSAP or SAP starting within 72 hrs.
 
3. PN avoided unless EN fails or is contraindicated
 
	NICE	Initial NBM N / Y From admission given trial of light diet. N / Y Initial NG or NJ? EN started within 72 hours if needed N / Y EN prescribed rate PN started if EN was not tolerated or contraindicated.
12	ERCP/ES	ERCP is indicated in patients with biliary pancreatitis and acute cholangitis within 48 hours of admission.	IAP	ERCP N / Y Indication: cholangitis or cholestasis When done? (hours)

\* Reference of guideline from which the QPI is primarily taken from

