## 5.5. Required data

Demographic details	
Age	Year of birth
Sex	Male/ Female/ Other
Ethnicity	European/ Pasifika/ Maori/ Asian/ Middle-Eastern/ Latin American/ African (MELAA)/ other ethnicity
Postcode	
Weight	kg
Height	cm
Smoking history	Current smoker /previous smoker /never smoker e-cigarette /cigarette
Admission details	
Date of first review by doctor/prescriber	Date (dd/mm/yyyy)  *From ED admission note
Time of first review by doctor/prescriber – as per admission note	24 hour clock time
Pancreatic enzymes at admission	Lipase/ Amylase/ Pancreatic amylase (tick one or more and give admission level and indicate what 3x upper limit is
Lipase/ amylase/ pancreatic amylase level	U/L
Epigastric pain confirmed on admission note	Yes/Non-epigastric abdominal pain/ No abdominal pain
Confirmation of AP diagnosis with imaging as per radiological report	MRI/ CT/ Abdominal USS
Charlson Comorbidity Index ( Appendix E )	Score out of 37
Aetiology	
Significant ETOH history investigated in first 72 hours	Yes - from medical history, Yes - ETOH blood test, No

Hypertriglyceridemia investigated in first 72 hours	Yes/No
Acute pancreatitis severity	
Predicted severity on admission as documented in clinical notes (72 hours)	Mild/ moderately severe/ severe
Method used to predict severity	Modified Glasgow/ Ransons'/ BISAP/ APACHE II/ SIRS/ CRP (>150)/ Other (please specify)/ Clinical judgement (no prediction tool)/ No prediction made.
Imaging	
CT assessment performed in the first 72 hours of presentation	Yes/ No
Indication for CT prior to 72 hours	Diagnostic uncertainty/ confirmation of severity based on clinical predictors of severe AP/ Failure to respond to conservative treatment or in the setting of clinical deterioration/ other (please specify)
Imaging of the gallbladder during admission	USS/ CT (gallstones seen on CT)/ MRI/ EUS/ prior imaging confirming gallstones/ previous cholecystectomy/ no imaging
Antibiotics	
Antibiotics administered in first 72 hours of presentation	Yes/ No
Indication for antibiotics	Cholangitis concomitant extrapancreatic infection/ prophylactic/ other – please state
Analgesia	
Simple analgesia (paracetamol/ NSAIDs) prescribed	Paracetamol/ NSAIDs/ Not charted
Simple analgesia frequency	regular/ PRN
Date simple analgesia first administered	Date (dd/mm/yyyy)

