Indication for NBM	for ultrasound scan/ for surgery/ for ERCP/ unknown reason/ other (please specify)
Patient tolerating PO oral intake (clear fluids) by 24 hours	Yes/no
Patient tolerating PO oral intake (clear fluids) by 48 hours	Yes/no
Patient tolerating PO oral intake (clear fluids) by 72 hours	Yes/no
Enteral feeding started in the first 72 hours?	Yes/no
Tolerating enteral feed	Yes/no
Type of Enteral feeding	NJ/NG
Rate of enteral feed	ml/hr
PN in the first 72 hours?	Yes/no
Rate of PN	ml/hr
Anticoagulation	
On regular anticoagulation therapy prior to admission	Warfarin/ dabigatran/ rivaroxaban/ other (please specify)/ Not on regular anticoagulation therapy
Regular anticoagulation continued on admission	Yes/No
(If yes) type of anticoagulation drug	warfarin/ dabigatran/ rivaroxaban/ other
Regular anticoagulation commenced on	Yes - at 24 hours/ Yes - at 48 hours/ No

admission	
Anticoagulation commenced on admission	Prophylactic-dose clexane/ treatment-dose clexane/ anticoagulation not started/ other (please specify)
Local complications in the days prior to the 30-day follow-up	
Necrotising pancreatitis ( Appendix B )	Yes/no
Acute necrotic collections (ANC)	Yes/no
Infected ANC	Yes/no
(If yes) intervention	Endoscopic/ percutaneous/ open necrosectomy
(if yes) date of intervention	Date (dd/mm/yyyy)
Acute pancreatic fluid collection (APFC)	Yes/no
Infected APFC	Yes/no
(if yes) intervention	Endoscopic/ percutaneous/ open necrosectomy
(if yes) date of intervention	Date (dd/mm/yyyy)
Portal/ splenic vein thrombosis	Yes/no
Other local complications	Pleuro-peritoneal fistula/ pleural effusion/ enteric fistula/ gastrointestinal bleeding/ pancreatic ascites/ arterial pseudoaneurysm/ other (free text)
Organ failure and other outcomes during the last 30-days follow-up	
Final aetiology	Alcoholic/ gallstone/ hypertriglyceridaemia/ others
Acute renal failure (as per RIFLE criteria - Appendix A )	Yes/no
Acute renal failure > 48 hours	Yes/no
ICU admission	Yes/no
(If yes) duration of ICU admission	day(s)
New renal dialysis required	Yes/no
(If yes) duration of dialysis	day(s)
New high-flow oxygen/ AIRVO requirement	Yes/no
Duration of high-flow/ AIRVO	days
Noninvasive ventilation required	Yes/no
(If yes) duration of noninvasive ventilation	days
Mechanical ventilation required	Yes/no

(If yes) duration of mechanical ventilation	day(s)
Inotropes required	Yes/no
(If yes) duration of inotropic support	day(s)

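### The second-line part of QPI 2 (aetiology) cannot be scored as Table 1 writes it: Section 5.5 has no field for IgG4 or drug causes, and the trigger can only be inferred

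*Protocol*

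**What the plan says.** Protocol Section 3, Table 1, row 2 sets the indicator as "All patients had tests for aetiology determined within 24 hours of admission". The metrics column gives two first-line elements, "U/S for gallstones ETOH history with intake (units per week, timing of binge to pain", and then a conditional step: "If both negative then lipids, IgG4, drugs".

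The aetiology block of Section 5.5 has two fields:

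- "Significant ETOH history investigated in first 72 hours", answered by source (history or blood test) or No.
- "Hypertriglyceridemia investigated in first 72 hours", answered Yes or No.

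The imaging block adds "Imaging of the gallbladder during admission", with the options "USS/ CT (gallstones seen on CT)/ MRI/ EUS/ prior imaging confirming gallstones/ previous cholecystectomy/ no imaging". The 30-day block adds a final aetiology field with the options "Alcoholic/ gallstone/ hypertriglyceridaemia/ others". Appendix B defines the first three of those labels.

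QPI 2 is one of the 12 rows behind the primary outcome of overall compliance (Section 4.1). It also feeds the by-domain hospital comparison (Section 4.2) and the comparisons of clinical outcome by compliance (Sections 2 and 8).

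**The concern.** A conditional indicator needs two kinds of data: whether the condition was met, and whether the conditional action was then taken. For QPI 2 the form supplies the first only indirectly and the second for one item of three. The gap falls on patients with neither gallstones nor an alcohol cause, the only group in whom the conditional step does any work. If the indicator is reported under its Table 1 wording, readers will take it that IgG4 and drug review were checked when they were not. The same would hold for the hospital funnel plots in this domain and for the split into compliant and non-compliant patients.

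**Working it through.** The protocol gives no figure on this point, so the check sets the metric beside the form.

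**Step 1. Each element of Table 1, row 2 against Section 5.5.**

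| Element | What Section 5.5 holds | Status |
|---|---|---|
| Ultrasound done | Imaging modality, any time in the admission | Recorded, untimed |
| Ultrasound result | None | Not recorded |
| Alcohol history taken | Yes, by source, 72-hour window | Recorded, wider window |
| Alcohol result, weekly intake, timing of binge | None | Not recorded |
| Lipids | Triglycerides only, Yes/No, 72-hour window | Recorded in part, wider window |
| IgG4 | None; the term appears only in Table 1 | Not recorded |
| Drug causes | None; the only pre-admission medicine items concern anticoagulants | Not recorded |

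Two of the three second-line items have no field. None of the seven elements can be placed inside the 24-hour window.

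**Step 2. Can the trigger be reconstructed?** In part.

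- The imaging field builds a positive result into its CT option and its prior-imaging option, but not into ultrasound, MRI or EUS.
- Under Appendix B, the gallstone label needs imaging confirmation, and the hypertriglyceridaemia label needs biliary and alcohol causes to have been excluded. So a final label of gallstone or alcoholic suggests the trigger was not met, and hypertriglyceridaemia or others suggests it was.

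This proxy fails in identifiable cases:

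- A negative first ultrasound followed by stones on MRI, EUS or CT ends as gallstone, although the second-line step had been triggered.
- The others label pools autoimmune, drug-related and unexplained cases with those whose first-line work-up was incomplete.
- Appendix B sets alcohol-induced disease at consumption above 10 g with no time limit, which need not match a positive significant history.
- The label is fixed at 30 days, not 24 hours.

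**Step 3. Direction of error.** Take patients truly negative on both first-line elements. Let F = first-line elements done, T = triglycerides tested, I = IgG4 sent, D = drug causes reviewed.

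- Pass under Table 1: F and T and I and D.
- Pass from the collected fields: F and T.

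Everyone who meets the first rule meets the second, so the form-based proportion cannot be lower. In this group:

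excess = P(F and T) × [1 − P(I and D | F and T)]

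The bracketed term has no observed data. The multiple imputation allowed in Section 8 cannot supply it, because a variable with no observed values cannot be imputed from this dataset.

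**Step 4. Carry-over to the primary outcome.** Section 4.1 does not say how overall compliance is formed.

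- All-or-none: a misclassified patient changes the result only if compliant on every other applicable QPI.
- Averaged over 12 applicable QPIs: one wrong item moves that patient's score by 1/12, about 8 percentage points.

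**The case against.** Several points on the other side are fair.

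- **The trigger.** A reader might infer that it cannot be determined at all. The documents do not support that: some imaging options carry a result, and the final aetiology label gives an approximate answer. What stands is that the trigger is not captured directly and that the proxy is retrospective. Even a perfect trigger would not supply IgG4 or drug data.
- **Direction.** A reader might infer that adherence will certainly be overstated. The protocol fixes no rule for elements that were not collected. Dropping them biases upward; counting them as not met would bias downward; treating them as missing leaves the step unscored. A statistical analysis plan, not shown here, may choose among these, but it cannot create the data.
- **Size.** It is tempting to assume that 20–40% of patients are negative for both causes and that IgG4 or drug review is omitted in 50–80% of them, giving 0.20 × 0.50 = 10% to 0.40 × 0.80 = 32% of the cohort wrongly passed. That product leaves out the chance of passing the items that are recorded. If that chance were 30–80%, the range would be 0.20 × 0.50 × 0.30 = 3% to 0.40 × 0.80 × 0.80 = 26%. None of these inputs is in the documents, so neither range is a finding.
- **Primary outcome.** Whatever the error in QPI 2, it does not pass unchanged into overall compliance, for the reason in step 4.
- **Evidence.** The REDCap form and Appendix D are not shown. The gap is established for the printed Required data list only.

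**Conclusion.** The point holds in limited form. As printed, Section 5.5 cannot score the second-line step of QPI 2: IgG4 and drug review have no field, and the condition that triggers them can only be approximated. This is a mismatch inside the protocol between a stated metric and the data it requires, so it cannot be left to the analysis stage.

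If the uncollected elements are dropped, the bias among patients negative for gallstones and alcohol is upward or nil, never downward. Its size cannot be estimated from the documents, and no particular effect on the primary outcome is shown. The conclusion assumes that the Required data list reflects the form in use. One of 12 indicators is affected, so this should be corrected but does not undermine the study as a whole.

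**What to change.** Add four items to the early form:

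- gallstones seen on first imaging (yes / no / not imaged);
- significant alcohol history (positive / negative);
- IgG4 sent (yes / no);
- drug causes documented as reviewed (yes / no).

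Mark each one, and the existing triglyceride item, as done within 24 hours of admission or not; without that flag the new items would still leave the deadline untestable. Score the second-line step only in patients negative on the first two items.

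If fields cannot be added, restate the QPI 2 metric as gallbladder imaging, alcohol history and triglycerides, within the windows actually collected. State in the protocol and the report that IgG4, drug review and the 24-hour deadline are not assessed.

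The first option costs a few REDCap entries from notes already under review. The second costs no data collection but yields a narrower indicator. Neither affects patient care.
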